[All participants will attend weekly sessions at the Baltimore VA annex. Participants in the intervention program will attend weekly group training sessions and those in the control group will attend weekly group health education classes. In order to avoid drop-out from the study, all participants will also keep an exercise log of home activity and they will be contacted by phone if they do not attend a weekly group session.

Furthermore participants will be reimbursed for parking for each weekly visit and an additional \$25 for the screening, enrollment, and the 12 and 24 week visits. This is important because many Veterans in Baltimore have limited income and the cost of travel and parking is a potential limitation to subject participation.

Upon completion of the initial 12 week intervention period the participants who had been randomized to the control group will be offered the exercise intervention for an additional 12 weeks (enrolled in the study for a total of 24 weeks). Due to concern regarding an unknown washout period those participants initially randomized to the intervention program cannot serve as their own controls but they will be followed without further intervention and reassessed at 4 week intervals (weeks 16, 20, 24) to gain additional information about what the length of the washout period might be.]

Balance exercise program

Subjects in the balance exercise program will participate in a three month exercise program designed to improve balance. Balance exercises will be performed three times per week in a home-based training program and participants will also attend a weekly group training session at which time participants will be instructed on the proper performance of the exercises and how to progress the exercises if appropriate. If a participant is unable to attend one of the weekly group sessions they will be contacted by phone and will continue the exercises performed in the previous week.

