Walking on toes/heels	10 steps Hold support	10 steps No support	10 steps Vary step length and width	10 steps Vary step speed	10 steps Vary light intensity	
Walking with varying step lengths and widths	10 steps Hold support	10 steps No support	10 steps Vary step speed	10 steps Step over objects	10 steps Vary light intensity	

The criterion for adequate compliance for a participant is to complete at least 75% of the balance training sessions. Several previously successful community and home based exercise programs were examined to determine what an expected level of compliance would be and how compliant a participant would need to be in order to observe an improvement in fall risk. One report of a multidimensional exercise program in community dwelling older adults showed that while performance on several balance scales improved significantly in both fully and partially (attended less than 75% of therapy sessions) adherent groups, the fully adherent group decreased their fall risk by 33% and the partially adherent group decreased their fall risk by 11% (89). Another study of a 12 week duration group-based exercise intervention that was found to significantly improve balance demonstrated a 78% attendance rate for group exercise sessions and 70% of the intervention participants attended at least three fourths of the sessions (90). In a study of diabetic patients there was a median exercise adherence of 87.5% over a 12 week training period (46). Interestingly, compared to these trials the "Feet First" trial of lower extremity exercise and walking on balance and fall incidence in diabetic neuropathy patients had only 45% protocol adherence in the intervention group and it was found that the degree of protocol adherence did not affect the trial results (48).

Participants will be given a balance exercise log to record the number of repetitions or steps completed of each exercise for each balance training session. Logs will be monitored and compliance assessed weekly. The goal is for participants to improve their balance and decrease their risk of falling. Balance and mobility will be assessed at base-line and 12 weeks.

Standard Care

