The SC group will be assigned an interventionist assessor for the duration of the study. This assessor will meet with the subjects during their orientation meeting and will be provided information about falls and recommendations for fall prevention. There will be no directed program throughout the study. [Participants in the standard care group will also meet in person on a weekly basis for general education class regarding health and fall prevention but will not participate in an exercise class. They will also be asked to keep a log of any exercise that they perform at home. This will attempt to control for the effects of coming into a facility once a week in both the standard care and balance exercise intervention.]

At the completion of the study participants in the standard care group will receive instruction in the balance exercise program so that they may benefit from the program as well.

Intervention Timeline

Initially enrollment will be slow to pilot the intervention program and will aim to enroll one or two participants. The next two waves of patients will include 4 to 6 participants and afterwards each wave will include approximately 8 participants. This will require approximately 48 months to complete the intervention for 55 participants.

Table 7: Intervention Program Timeline:

Group (n)	Months																	
	1-3	4-6	7-9	10-12	13-15	16-18	10-21	22-24	25-27	28-30	31-33	34-36	37-39	40-42	43-45	46-48	49-51	52-54
1 (1 - 2)	x	x																
2 (4 - 6)			x	x														
3 (4 - 6)					x	x												
4 (8)							x	x										
5 (8)									x	x								
6 (8)											x	x						
7 (8)													x	x				
8 (8)														x	x			
Recruitment	x	x	x	x	x	x	x	x	x	x	x	x	x	x	x	x		
Screening	x	x	x	x	x	x	x	x	x	x	x	x	x	x	x	x	x	
Enrollment	x	x	x	x	x	x	x	x	x	x	x	x	x	x	x	x	x	
Outcome Assessment			x	x	x	x	x	x	x	x	x	x	x	x	x	x	x	x

Data management

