The participants in the study will not be blinded to their group assignment since the intervention is an exercise intervention that requires active participation in both group and home exercise programs. However, the individuals performing the pre and post intervention assessments will be different individuals than those who lead the weekly group exercise sessions and are in regular contact with the participants. These assessors will be blinded to the participant's group assignment and will follow standardized protocols to perform and record the participants' performance on the outcome measures. To ensure that potential bias is minimized standardized instructions will be given to the participants and established protocols will be followed for measurement of the FSST (14) and DGI (15, 91). Assessment of the DGI on the GaitRite and the assessments performed on the ActiveStep are computerized measurements that will be automated.

Independent Data and Safety Monitoring Plan (DSMP)

The University of Maryland Institutional Review Board (UMIRB) and the Baltimore VA R&D committee will review the proposed level of risk and monitoring plan. All serious adverse events (SAEs) will be reported to the UMIRB and the VA R&D committee. The IRB will perform an annual review that may include any of the

following: adverse events (AEs), enrollment numbers, procedure reports, raw data, outcomes (primary, secondary), and preliminary analyses.

A data safety monitoring board (DSMB) will meet every six months or more frequently if a safety review is required. The DSMB will perform an unblinded review of adverse events, protocol deviations and changes, and enrollment numbers. Due to concerns regarding repeated testing for significance and given that this is a pilot study; interim analyses for efficacy will not be performed. Reasons for early termination of the trial will include an increased rate of serious adverse events related to the intervention or severe logistical or data quality problems that would make completion of the trial unfeasible.

Potential problems and limitations of the planned protocol

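### Falls during the study are not prospectively recorded in either arm, so the DSMB's adverse-event review may miss or under-count them

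*Combined protocol and SAP*

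**What the plan says.** **Monitoring.** The Independent Data and Safety Monitoring Plan states: "A data safety monitoring board (DSMB) will meet every six months or more frequently if a safety review is required". It continues: "The DSMB will perform an unblinded review of adverse events, protocol deviations and changes, and enrollment numbers". It also states: "All serious adverse events (SAEs) will be reported to the UMIRB and the VA R&D committee". On stopping it says: "Reasons for early termination of the trial will include an increased rate of serious adverse events related to the intervention", and adds severe logistical or data quality problems. It gives no threshold, comparator or attribution rule.

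**What is recorded.** Table 2 (testing scheme) and Table 4 (hypothesis testing plan) contain no fall count or fall diary. In the Balance exercise program section: "Participants will be given a balance exercise log to record the number of repetitions or steps completed". Under Standard Care, the control log covers exercise done at home. Falls enter the plan as history only: as the stratification factor, as a baseline covariate, and as the grouping variable in exploratory hypothesis 2. No section says whether a fall is an adverse event.

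**Contacts.** Under Intervention Programs, both arms have weekly contact and weekly group sessions, and all participants keep a home log. After week 12 the exercise arm receives no further intervention and is reassessed at weeks 16, 20 and 24.

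**Controls after week 12.** Intervention Programs says "participants who had been randomized to the control group will be offered the exercise intervention for an additional 12 weeks". Standard Care says "At the completion of the study participants in the standard care group will receive instruction in the balance exercise program", and item 4 of the limitations section likewise places this at the end of the study.

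**The concern.** Falling is both the outcome the trial hopes to improve and a foreseeable hazard of the intervention. Participants have autonomic neuropathy, which the Background links to falls. They exercise at home three times a week, and Table 6 allows progression to unsupported, eyes-closed and obstacle-stepping tasks.

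A DSMB can weigh only what reaches it. With no fall question, definition or log entry, a non-serious fall at home is known only if the participant happens to mention it. The one safety ground named for stopping then requires an event to be both serious and judged related, which leaves very few events at this sample size.

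There is a second loss. The Background section on reducing falls says the pilot should inform the powering of a later trial. Fall rates by arm are an obvious input to that, and as written they will not exist.

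**Working it through.** The monitoring plan contains no number to reproduce. The arm sizes come from the sample size section, so I checked those first.

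**Step 1: arm sizes.** A two-sided two-sample t test with difference 2.0 s, SD 2.34 s, alpha 0.05 and power 0.80 gives n = 22.49, rounded up to 23 per group, with power 0.809. This matches Table 3. For standard care, 23/0.90 = 25.6, so 26. The plan states 29 for exercise, and 26 + 29 = 55. These figures are not in dispute.

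**Step 2: inputs for fall counts.**
- Low annual proportion: 9/44 = 20.45% (Preliminary Studies). The look-back period is not stated; one year is my assumption.
- High annual proportion: one third (Background, Risk of falls). That figure is for age 65 and over, while this trial enrols ages 50 to 70.
- Share of falls that are serious: not in the documents. Assumed 10%, range 5% to 20%.
- Constant fall rate, independent events, no dropout (assumed).

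**Step 3: expected events in weeks 1-12.** Annual rate r = -ln(1 - p); 12-week rate = r x 12/52; 12-week risk = 1 - exp(-rate).

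| | p = 20.45% | p = 1/3 |
|---|---|---|
| r per year | 0.2288 | 0.4055 |
| 12-week rate | 0.0528 | 0.0936 |
| 12-week risk | 5.1% | 8.9% |
| Control fallers (x 26) | 1.3 | 2.3 |
| Risk if exercise doubles the rate | 10.0% | 17.1% |
| Exercise fallers (x 29) | 2.9 | 4.9 |
| Falls as events (29 x 2 x rate) | 3.06 | 5.43 |
| Serious falls at 10% | 0.31 | 0.54 |
| P(at least one serious fall) = 1 - exp(-expected) | 26% | 42% |

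With a serious share of 5% to 20%, that last probability runs from 14% to 66%. Even with a true doubling, and with every serious fall judged related, there may be no serious fall at all. By construction, counting every fall gives ten times as many events at the 10% share.

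**Step 4: could complete fall counts support a test?** I enumerated the exact binomial distributions for 29 against 26 with a one-sided 5% Fisher test. Power for a doubling is 4.9% (low rate) and 11.5% (high rate). For a tripling it is 16% and 32%. Under a true doubling, the exercise arm would still show an equal or lower faller proportion 29% (low rate) or 19% (high rate) of the time.

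**Step 5: effect of pooling over 24 weeks.** Suppose exercise doubles the rate while it lasts, with no carry-over, and a fraction u of controls takes it up in weeks 13-24. The ratio by original arm is (2 + 1)/(1 + 1 + u):
- u = 0: 3/2 = 1.5
- u = 0.5: 3/2.5 = 1.2
- u = 1: 3/3 = 1.0

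In weeks 1-12 alone it stays at 2.0. Pooling therefore dilutes a difference to the extent that controls take up exercise; splitting by period does not.

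**The case against.** The strongest reply is that the monitoring plan is broader than its stopping sentence. The DSMB's adverse-event review is unblinded and not restricted to serious or related events. It can meet early, and every SAE goes to the IRB and the R&D committee. The termination reasons are introduced as inclusions, not as a closed list. Exercise starts with hand support, a trainer decides progression each week, and severe autonomic neuropathy is excluded. All of this stands.

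It rules out three stronger readings that a reader might infer:
- That the DSMB could not see falls caused by exercise. Any fall reported as an adverse event would be open to its unblinded review.
- That a fall on a non-exercise day would automatically be set aside as unrelated. The documents give no attribution rule in either direction.
- That the week-12 offer hides harm. Weeks 1-12 remain a randomised contrast of exercise with no exercise. Dilution needs pooling over 24 weeks, which no section prescribes, and uptake of an offer whose timing is itself contradictory.

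A second reply is that 55 participants cannot settle a fall difference. That is also right. It argues against a formal boundary, but not against recording the events. None of these replies supplies a way for a non-serious fall at home to be asked about, defined or logged.

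**Conclusion.** The point holds as a gap in ascertainment. On-study falls are not systematically collected in either arm, and their status as adverse events is undefined. The only safety ground named for termination depends on serious events judged related. The DSMB may therefore miss or under-count falls, especially non-serious ones during home exercise, and the pilot will not provide fall rates by arm.

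The affected numbers are small: about 1 to 2 control fallers in 12 weeks, against 3 to 5 in the exercise arm if the rate doubled. These counts rest on the assumed one-year window for the pilot figure, an older population for the upper figure, and a constant rate. The serious-fall figures rest also on an assumed serious share. The gap in collection rests on none of these. This is worth correcting because it is cheap; it does not show that the trial is unsafe or its primary comparison invalid.

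**What to change.** 1. Add a dated fall and injury line to the home log that both arms already keep.
2. Ask the same scripted fall question in both arms at the existing weekly contacts and at follow-up visits, including weeks 16, 20 and 24 for the former exercise arm.
3. State in the protocol whether and when a fall is recorded as an adverse event.
4. Give the DSMB a table of all falls and all SAEs by randomised arm, regardless of attribution, with weeks 1-12 shown separately from weeks 13-24. State that it is descriptive, given power of about 5% to 12% for a doubling.
5. Reconcile Intervention Programs with Standard Care and limitation 4 on when controls receive the exercise programme. Which version applies is for the sponsor to decide; the DSMB table should follow it.

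No change to the termination reasons and no statistical boundary is proposed. The cost is one log line, one question and one split table, with no added visits or participants. The downside is some extra adverse-event recording for mild falls.
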